## **I. Abstract**

This prospective randomized trial aims to compare two umbilical closure techniques for trocar site hernia (TSH) in laparoscopic cholecystectomy. A prospective randomized study will be performed including consecutive patients who underwent an elective laparoscopic cholecystectomy for symptomatic cholelithiasis during the 18 months.

## **II. Background and Significance/Preliminary Studies**

Laparoscopic cholecystectomy is currently the gold standard in the treatment for symptomatic cholelithiasis that offers a variety of advantages over conventional open surgery such as shorter recovery time, better cosmesis, less wound complication rates, and less pain. Despite these advantages, LC can result in unique complications. Among these complications, trocar site hernia (TSH) is one of the most important complications because laparoscopic cholecystectomy promises smaller abdominal incisions and better cosmetic outcomes. A second surgical intervention due to TSH may overshadow the gains of the previous laparoscopic surgery. In studies conducted to date, the rate of trocar hernia in laparoscopic cholecystectomy has been presented at very different rates. Many studies have shown that the most frequent site of TSH is the umbilical trocar site. To avoid this important complication of laparoscopic cholecystectomy, many different techniques have been described to date for trocar port fascia repair. Most of these techniques require special devices. In addition, a few studies compare these techniques with standard fascial closure, which is mostly used by surgeons.

## **III. Study Aims**

We hypothesized that the fascial closure of the umbilical trocar incision under the intraabdominal vision with the laparoscopic camera could be reduced TSH. This prospective randomized controlled study aims to assess whether fascial closure of umbilical trocar site under direct laparoscopic vision in LC can reduce the incidence of TSH.

## **V. Study Design**

All consecutive patients with symptomatic cholelithiasis who underwent elective LC between January 2020 and June 2021 will be considered for enrolment in the study.

Patients who required urgent surgery due to acute cholecystitis will be excluded. The other exclusion criteria will be age under 18 years, previous umbilical hernia repair, and pre-existing umbilical hernia. All patients who enrolled in the trial will be provided an informed consent form

The sample size calculation was based on the data of a previous study. TSH rate was 6.6% in patients who underwent laparoscopic cholecystectomy. With a statistical power of 80% and a significance level of  $p < 0.05$ , the required sample size was 92 patients. Statistical analysis was performed using IBM SPSS Statistics version 20.0 (SPSS Inc., Chicago, IL, 2011) for Windows. Results were compared by the Student-t test or Mann-Whitney-U test for continuous variables and Chi-square or Fisher exact tests were used for categorical variables. A p-value  $< 0.05$  was considered to represent statistical significance.

The primary outcome endpoint in the study is the presence of a TSH. Secondary endpoints are operative complications, wound infection, hematoma, pain, and length of hospital stay. Patients will be evaluated by clinical examination. If the surgeon suspected a TSH, abdominal ultrasound and/or abdominal computed tomography will be carried out. Any wound hematoma will be considered as a postoperative complication when they limited daily activities or required drainage. Wound infection will be defined as the presence of pain, redness, and purulent discharge at the umbilical trocar incision.

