## **VI. Study Procedures**

All consecutive patients with symptomatic cholelithiasis who underwent elective LC between January 2020 and June 2021 will be considered for enrolment in the study. Patients who required urgent surgery due to acute cholecystitis will be excluded. The other exclusion criteria will be age under 18 years, previous umbilical hernia repair, and pre-existing umbilical hernia.

Operations will be performed by four experienced surgeons. A supraumbilical transverse skin incision followed by an open technique with a vertical incision will be performed. Four trocars will be used. One 10-mm trocar was placed, and pneumoperitoneum will be obtained. A 30-degree endoscope will be inserted through this trocar. One 10-mm trocar (at the epigastrium) and two 5-mm trocars (at the right subcostal and lower right quadrant) were inserted under direct visualization. The gallbladder will be removed through the umbilical incision with an endo bag. The umbilical incision will be enlarged if needed to be for extraction of the gallbladder. After the extraction of the gallbladder, the size of the fascial defect will be measured directly using a ruler. The method of umbilical fascial closure for each patient will be determined using the computerized random generation of a number just before the operation. The number was given to the surgeon and the previously assigned umbilical fascial closure technique (assigned to that number) will be used. Patients will be randomly assigned to the umbilical closure non-video-assisted (UC) and umbilical closure with video-assisted (UCVA) groups.

In the UC group, the umbilicus incision will be closed with an interrupted suture with synthetic absorbable 0 suture (Pedesente®, Dögsan A.S., Trabzon, Turkey). In the UCVA group, the laparoscope will be inserted the epigastric trocar and the umbilical fascial defect will be visualized intraabdominal. Then the defect will be closed an interrupted suture with synthetic absorbable 0 suture (Pedesente®, Dögsan A.S., Trabzon, Turkey) including all layers of the abdominal wall under the direct reverse vision of the defect with a 30° laparoscopic camera.

The skin closure will be performed using a 3/0 polypropylene suture (Sterilen®, Dögsan A.S., Trabzon, Turkey). Patients' operative characteristics will be recorded after the operations.

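### 92 patients split equally do not give the stated 80% power with either planned test: even at 6.6% v 0% TSH, exact power is 36% (chi-square) or 8% (Fisher) two-sided, and 59% or 19% one-sided

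*Protocol*

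**What the plan says.** All of the sample size reasoning is in one paragraph of section V, Study Design. It cites a previous study in which "TSH rate was 6.6% in patients who underwent laparoscopic cholecystectomy", continues "With a statistical power of 80% and a significance level of" 0.05, and concludes that "the required sample size was 92 patients". The same paragraph says that "Chi-square or Fisher exact tests were used for categorical variables", and that a p-value below 0.05 "was considered to represent statistical significance".

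The endpoint is binary: "The primary outcome endpoint in the study is the presence of a TSH". Section III asks whether closure under laparoscopic vision "can reduce the incidence of TSH". Section VI describes two arms ("Patients will be randomly assigned to the umbilical closure non-video-assisted (UC) and umbilical closure with video-assisted (UCVA) groups") without an allocation ratio. The protocol does not give the TSH rate expected with UCVA, the sidedness of the test, the number per arm or the formula used.

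**The concern.** A sample size for comparing two proportions needs two rates, and only one is given. That gap alone could be filled in an analysis plan that is not shown. The real difficulty is that the protocol attaches a definite power to a definite number of patients and names the tests. The claim can therefore be checked against its most favourable case, a UCVA rate of 0%, since no larger reduction from 6.6% is possible.

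If the claim fails there, the primary comparison is credited with a power it does not have. A non-significant result would be the likely outcome even for a technique that prevented every hernia. Set beside a stated 80% power, that result invites the reading that the two closures do not differ.

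**Working it through.** **Inputs.** From section V: rate 6.6%, power 80%, alpha 0.05, 92 patients, chi-square or Fisher. Assumed, because unstated: 6.6% is the UC rate; 92 is the total, split 46:46; the UCVA rate is 0%, with higher rates also shown. Both sidednesses are worked.

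**Step 1: reproduce 92.** The arcsine formula is n per arm = 2(z_alpha + z_power)² / h², with h = 2·arcsin√p1 − 2·arcsin√p2. For 6.6% v 0%, h = 0.5196.

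- One-sided: 2(1.645 + 0.842)² / 0.5196² = 45.8, so 46 per arm and **92 in total**.
- Two-sided: 2(1.960 + 0.842)² / 0.5196² = 58.1, so 59 per arm and 118 in total.
- One-sided, UCVA rate 0.1% instead of 0%: 59.4, so 60 per arm. At 1%: 121.3, so 122 per arm.

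The pooled normal formula for 6.6% v 0% gives 114 per arm two-sided and 90 one-sided, so it does not return a total of 92. The stated figure thus comes back exactly only from a one-sided arcsine calculation against exactly 0%. That approximation is poor at a zero rate, as the jump from 46 to 60 per arm for a 0.1-point change shows.

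**Step 2: what each test needs at 46 v 46.** With a hernias in UC and none in UCVA, the uncorrected chi-square statistic is 92a/(92 − a).

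- a = 3: 276/89 = 3.10, two-sided p = 0.078 (one-sided 0.039).
- a = 4: 368/88 = 4.18, two-sided p = 0.041.
- Fisher, a = 4: one-sided p = 0.058.
- Fisher, a = 5: two-sided p = 0.056 (one-sided 0.028).
- Fisher, a = 6: two-sided p = 0.026.

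**Step 3: exact power at 6.6% v 0%.** With no UCVA hernias, power is P(X ≥ r) for X ~ Binomial(46, 0.066), where r is the smallest significant count. The expected count is 46 × 0.066 = 3.04.

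| Test | r | Power |
|---|---|---|
| Chi-square, two-sided | 4 | 36.1% |
| Fisher, two-sided | 6 | 8.1% |
| Chi-square, one-sided | 3 | 59.3% |
| Fisher, one-sided | 5 | 18.5% |

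**Step 4: UCVA rate above 0%.** Here every pair of counts was enumerated, with 46 per arm (chi-square / Fisher).

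| UCVA rate | Two-sided | One-sided |
|---|---|---|
| 1% | 25% / 5% | 43% / 13% |
| 3.3% (halving) | 11% / 2% | 20% / 5% |

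**Step 5: other readings of 92.**

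- *Unequal split of 92 in total, v 0%.* Over splits from 5:87 to 87:5, the two-sided maximum is 72.7% for chi-square (19 UC : 73 UCVA) and 39.1% for Fisher (34:58). A one-sided chi-square passes 80% only at 24:68 and 25:67, where a single UC hernia against none would count as significant.
- *92 per arm, two-sided (chi-square / Fisher).* 86% / 57% v 0%; 78% / 52% v 0.2%; 52% / 34% v 1%; 16% / 9% v 3.3%.
- *92 per arm, one-sided.* 95% / 73% v 0%; 91% / 68% v 0.2%; 72% / 49% v 1%.

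**Step 6: sizes that do give 80%.** Against 0%, the smallest equal arms with exact power of at least 80% are 83 (chi-square) or 119 (Fisher) two-sided, and 64 or 101 one-sided. For a halving to 3.3%, the pooled two-sided normal formula gives 677.03, so 678 per arm.

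**The case against.** The strongest reply is that 92 is not an arithmetic slip. It follows from a recognised formula, and section III states a directional hypothesis, which fits a one-sided calculation. This stands as an explanation but does not rescue the claim: the one-sided setting and the 0% rate are unstated, and exact one-sided power with the named tests is 59% or 19%.

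A second reply is that the allocation and the per-arm number are also unstated, and some readings do reach 80%: 92 per arm with chi-square, or a one-sided chi-square at about 25:67. This is correct, so the conclusion has to be tied to 92 in total, split equally. But the text says 92 patients without mentioning groups, nothing suggests a 25:67 split, and Fisher falls short on every reading. With about 3 events expected, the expected hernia count is near 1.5 per arm. That is below 5, where Fisher is the usual choice.

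Third, section V does not say that 6.6% is the UC rate. That is the natural reading, but it is an assumption.

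Finally, enrolment is defined by an 18-month window of consecutive patients, so 92 is not a cap, and how a null result would be read is a prediction. Both points are fair. The chances of a non-significant result apply to a trial of 92, which is the size for which the protocol makes its power claim.

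**Conclusion.** The concern holds. With 92 patients split equally and 6.6% as the UC rate, the stated 80% is not reached by either planned test, even if UCVA prevents every hernia. The shortfall is at least 20 percentage points (one-sided chi-square, 59%) and as much as 72 (two-sided Fisher, 8%). Under complete prevention, a two-sided analysis would be non-significant 64% (chi-square) or 92% (Fisher) of the time. Because 0% is the most favourable rate, these powers are ceilings for 46 per arm.

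Reading 92 as a per-arm number rescues a two-sided claim only for essentially complete prevention with an uncorrected chi-square. One-sided, it tolerates a rate of 0.2% but not 1%, and again only with chi-square. The fault is a power figure that does not carry over to the named tests, not merely missing detail, so an analysis plan could not make the sentence true. It bears on the primary endpoint and must be corrected.

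**What to change.** In section V, withdraw the 80% claim. State the assumed UC and UCVA rates, the sidedness, the allocation and the test behind the power figure, then give the exact power. If 1:1 and two-sided were meant, the text could read:

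> Assuming a TSH rate of 6.6% with UC, two-sided alpha of 0.05 and 1:1 allocation, 92 patients (46 per arm) give exact power of 36% (chi-square) or 8% (Fisher) if UCVA prevents all TSH, and 11% or 2% if it halves TSH. A non-significant result will not be read as no difference.

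If one-sided was meant, the figures are 59% or 19%, and 20% or 5%. If 92 per arm was meant, say so and use 86% or 57%, and 16% or 9%, two-sided; one-sided against 0% the figures are 95% or 73%.

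The cost is wording only: a less favourable stated power and no extra patients. This corrects the statement but leaves the trial underpowered. Keeping 80% two-sided would instead need 166 patients (chi-square) or 238 (Fisher) in total, and then only for complete prevention.

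### The primary hernia comparison may use chi-square or Fisher, which can disagree at plausible low counts; naming the Boschloo test would settle the choice and gain power over Fisher at little cost (minor)

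*Protocol*

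**What the plan says.** All of the relevant text except the aim and the allocation is in Protocol section V, Study Design.

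- Endpoint: "The primary outcome endpoint in the study is the presence of a TSH". It is binary.
- Test: one sentence covers all categorical variables, "Chi-square or Fisher exact tests were used for categorical variables". It does not single out TSH, give a rule for choosing between the tests, or say whether chi-square carries a continuity correction.
- Event rate: "TSH rate was 6.6% in patients who underwent laparoscopic cholecystectomy". No rate is given for the video-assisted (UCVA) arm. Section III asks whether the technique "can reduce the incidence of TSH", so a reduction is expected.
- Size: "With a statistical power of 80% and a significance level of" 0.05, "the required sample size was 92 patients". Whether 92 is a total or a per-arm number is not said.
- Allocation (section VI, Study Procedures): "Patients will be randomly assigned to the umbilical closure non-video-assisted (UC) and umbilical closure with video-assisted (UCVA) groups". No ratio is stated.

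**The concern.** At 6.6%, the conventional-closure (UC) arm would see about 0.066 × 46 = 3.0 hernias if 92 is the total, or 0.066 × 92 = 6.1 if it is per arm. At such counts uncorrected Pearson and Fisher can fall on opposite sides of 0.05. Whoever runs the analysis could report either and be within the protocol, and the verdict on the only primary endpoint could turn on that choice.

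The usual way out is to use Fisher when an expected count is below 5. That removes the freedom but, at 46 per arm, settles on a test whose true error rate is far below 5%. A valid exact test exists that gives up less power.

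**Working it through.** **Inputs.** From section V: binary endpoint, control rate 6.6%, level 0.05, 92 patients. Assumed because not stated: 1:1 allocation, two-sided testing, n = 46 or n = 92 per arm, UCVA rate between 0% and 6.6%.

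**The plan's own figure.** The 92 cannot be derived from the protocol's inputs, because only one rate is given. It is reached only with added assumptions: for example, one-sided with 0% in the UCVA arm, the arcsine formula gives 46 per arm (92 in total) and the pooled formula 90 per arm. Two-sided, 6.6% v 0% needs 114 per arm. Both readings of 92 are therefore carried through.

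**Step 1: single tables.** With a and b events in arms of size n and pooled rate p = (a + b)/(2n), Pearson is X² = ((a − b)/n)² / (p(1 − p)·2/n). For 4 v 0 at n = 46:

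- Pearson: p = 4/92 = 0.0435, so X² = 0.007561/0.001808 = 4.18 and the P value is 0.041.
- Continuity-corrected: replace 4/46 by 3/46, so X² = 0.004253/0.001808 = 2.35 and the P value is 0.125.
- Fisher: 2 × C(46,4)/C(92,4) = 2 × 163185/2794155 = 0.117.

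The Boschloo P value uses Fisher's P as the statistic and takes the largest null probability over the common rate. At n = 46:

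| Events | Pearson | Corrected | Fisher | Boschloo |
|---|---|---|---|---|
| 3 v 0 | 0.078 | 0.240 | 0.242 | 0.175 |
| 4 v 0 | 0.041 | 0.125 | 0.117 | 0.076 |
| 5 v 0 | 0.0215 | 0.066 | 0.056 | 0.035 |
| 6 v 1 | 0.049 | 0.116 | 0.111 | 0.076 |
| 7 v 1 | 0.026 | 0.064 | 0.059 | 0.039 |

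At n = 92, Pearson and Fisher split at 4 v 0 (0.043, 0.121), 5 v 0 (0.023, 0.059) and 7 v 1 (0.030, 0.064). They agree at 6 v 0 (0.013, 0.029) and at 6 v 1 (0.054, 0.118).

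**Step 2: how often the verdicts differ.** Sum Bin(a; n, 0.066) × Bin(b; n, UCVA rate) over all tables where exactly one of uncorrected Pearson and Fisher gives P < 0.05:

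| UCVA rate | 46 per arm | 92 per arm |
|---|---|---|
| 0% | 28% | 29% |
| 2% | 14% | 12% |
| 3.3% | 9% | 6% |
| 6.6% (null) | 5% | 2% |

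The 0% row can be checked by hand, because b is always 0. At n = 46 the split tables are 4 v 0 and 5 v 0, with probabilities 0.176 + 0.104 = 0.280. At n = 92 they are again 4 v 0 and 5 v 0: 0.130 + 0.162 = 0.292.

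**Step 3: true type I error at nominal 5%.**

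| | Pearson, uncorrected | Fisher | Boschloo |
|---|---|---|---|
| 46 per arm, common 6.6% | 5.9% | 1.1% | 2.6% |
| 46 per arm, maximum | 6.1% | 3.0% | 4.7% |
| 92 per arm, common 6.6% | 4.6% | 2.4% | 3.7% |
| 92 per arm, maximum | 5.2% | 3.6% | 4.99% |

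**Step 4: power of Fisher and Boschloo.** At 6.6% v 0%, Fisher needs at least 6 v 0 and Boschloo at least 5 v 0, at either sample size.

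- 46 per arm: P(X ≥ 6) = 8% for Fisher, P(X ≥ 5) = 19% for Boschloo.
- 92 per arm: 57% and 73%.
- 92 per arm, 6.6% v 2%, by full enumeration: 20% and 28%.

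**The case against.** Four objections carry weight.

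1. *The tests agree at the most likely tables.* True: for 6.6% v 0% these are 3 v 0 at 46 per arm (neither significant) and 6 v 0 at 92 per arm (both significant). A reader might infer from the split tables that the tests conflict at the expected counts, or over most of the plausible range. They do not: they agree in at least 71% of trials in every scenario computed, and the 28% and 29% belong to a UCVA rate of exactly 0%, which the protocol never states.

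2. *The split needs an uncorrected chi-square.* True. The corrected version differs from Fisher in at most 0.1% of trials at 46 per arm and 0.5% at 92. The protocol does not exclude the uncorrected version, so the ambiguity is real but limited.

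3. *The wording most naturally means the expected-count rule, and such a rule is SAP detail.* The missing rule alone would indeed be no finding. At 46 per arm the rule's verdict differs from Fisher's in at most 0.3% of trials, so under that reading the freedom to choose all but disappears. What is left is Fisher's conservatism.

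4. *Boschloo is a preference.* Partly true. A reader might infer that neither permitted test is acceptable, but Fisher is valid and Pearson's worst error rate is 6.1%. Naming either test in advance would also remove the ambiguity. The case for Boschloo is that it is valid and gains power over Fisher. Asking merely for an unconditional exact test would be too loose: at 4 v 0 with 46 per arm, Boschloo gives 0.076 and Barnard 0.047.

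**Conclusion.** The point holds as a minor improvement. Section V permits two tests for a rare binary primary endpoint. If chi-square is uncorrected, the choice can decide significance in roughly 2% to 29% of trials, depending on the unstated UCVA rate and on whether 92 is a total or per arm. If the expected-count rule was meant, the test at 46 per arm is in effect Fisher, which is valid but runs well below its nominal level.

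A reader might infer that Fisher always costs more than half of the attainable power. That holds at 46 per arm for 6.6% v 0% (8% against 19%). At 92 per arm the loss is about a fifth: (73 − 57)/73 = 22%.

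Nor does the choice of test rescue the design. At 46 per arm Boschloo reaches only 19% for the most favourable effect and 5% for 6.6% v 3.3%; that shortfall is a separate issue.

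These results assume 1:1 allocation, two-sided 0.05, a 6.6% control rate, and every patient contributing a yes/no outcome.

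**What to change.** In section V, add one sentence naming the two-sided Boschloo (Fisher–Boschloo unconditional exact) test at 0.05 as the single test for TSH, with the risk difference and its 95% score interval reported alongside. Leave chi-square or Fisher for the other categorical variables.

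The cost is that sentence and, if SPSS 20 does not offer the test, one call in free software. No patient, visit or sample size changes. The downside is that, at 46 per arm, 4 v 0 or 6 v 1 (both P = 0.076) would not be significant, as either could be under uncorrected Pearson.

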#### *Follow-up*

All patients will be scheduled to return for an outpatient visit in the second week and every three months after the surgery.

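### The primary endpoint depends on a surgeon's suspicion, and nothing in the visible protocol stops that surgeon from being the operator who knows the arm

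*Protocol*

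**What the plan says.** Protocol section V (Study Design) makes the presence of a TSH the primary endpoint. On ascertainment it says "Patients will be evaluated by clinical examination" and then "If the surgeon suspected a TSH, abdominal ultrasound and/or abdominal computed tomography will be carried out". No imaging is planned for a patient in whom no hernia is suspected.

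Section VI (Study Procedures) describes the only surgeons in the protocol: "Operations will be performed by four experienced surgeons". Allocation is passed on at the operation: "The number was given to the surgeon and the previously assigned umbilical fascial closure technique" is then used, so the operator knows the arm. The same section says that patients' "operative characteristics will be recorded after the operations". It gives one skin closure, with no difference by arm.

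The Follow-up paragraph fixes the timing, "All patients will be scheduled to return for an outpatient visit in the second week and every three months after the surgery", but names neither an examiner nor an end of follow-up.

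None of these sections mentions masking of the examiner, requires the examiner to be someone other than the operator, or keeps the operative record from the examiner.

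**The concern.** A patient becomes a case only if a surgeon first suspects a hernia. That suspicion is a judgement, and the text allows it to be formed by someone who performed the closure and knows which technique was used. Section III (Study Aims) states a directional hypothesis, that closure under laparoscopic vision reduces TSH. An examiner who shares that expectation might look harder in one arm. One keen to find failures of the newer technique might do the opposite.

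The endpoint is rare, so a few such judgements matter. At the protocol's own rate of 6.6%, about three hernias are expected per arm if 92 is the total sample and about six if it is per arm. One or two found or missed because the arm was known would change the estimated effect materially. No analysis can restore masking once the visits have taken place, so this belongs in the protocol.

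**Working it through.** **What the text establishes**

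1. Imaging requires a surgeon's suspicion (section V).
2. The operating surgeon knows the arm (section VI).
3. The follow-up examiner is not identified (Follow-up).
4. No visible sentence masks the examiner or separates examiner from operator.

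The text does not say that the operator examines; it permits it. The protocol gives no figure for detection, so there is none to reproduce. What follows shows how large the bias could be under stated assumptions.

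**Inputs**

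- True TSH rate 6.6% in both arms, that is, no treatment effect. The 6.6% is from section V.
- Detection per examination of 80% in UC and 60% in UCVA. Both are assumed and neither is in the documents.
- Arm size 46 or 92. Section V says "the required sample size was 92 patients" without saying whether this is the total or per arm.
- Chi-square and Fisher exact tests, both named in section V, two-sided at 0.05.

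Expected true hernias per arm: 46 × 0.066 = 3.0; 92 × 0.066 = 6.1.

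**Estimated effect after a single examination**

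- UC: 0.066 × 0.80 = 5.28%.
- UCVA: 0.066 × 0.60 = 3.96%.
- Apparent risk ratio: 3.96 / 5.28 = 0.75. With the detection rates swapped it is 1.33. With equal detection it is 1.00.

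**Repeat examinations**

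The schedule gives five visits in the first year (week 2 and months 3, 6, 9 and 12), so a hernia may be present at one to five of them. If examinations are independent, detection after k of them is 1 − (1 − d)^k.

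| k | UC | UCVA | Apparent risk ratio | Reversed |
|---|---|---|---|---|
| 1 | 0.800 | 0.600 | 0.75 | 1.33 |
| 2 | 0.960 | 0.840 | 0.88 | 1.14 |
| 4 | 0.998 | 0.974 | 0.98 | 1.02 |
| 5 | 0.9997 | 0.990 | 0.99 | 1.01 |

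**False-positive rate**

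This is the exact probability of p < 0.05, summed over both binomial distributions. Chi-square is without continuity correction.

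| Detection, UC v UCVA | 46/arm Fisher | 46/arm chi-square | 92/arm Fisher | 92/arm chi-square |
|---|---|---|---|---|
| 70% v 70%, one look | 0.5% | 4.7% | 1.8% | 4.2% |
| 80% v 60%, one look | 0.7% | 5.6% | 2.8% | 6.0% |
| 80% v 60%, four independent looks | 1.1% | 5.9% | 2.4% | 4.6% |
| Full detection, both arms | 1.1% | 5.9% | 2.4% | 4.6% |

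The 70% v 70% row has the same average detection as 80% v 60%, so comparing those two rows isolates the effect of unequal detection.

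**A wider assumed gap**

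With 90% v 50% at one look, the observed rates are 5.9% and 3.3%, a risk ratio of 0.56 (1.80 reversed). At 92 per arm the false-positive rate is 6.3% (Fisher) or 11.7% (chi-square), against 2.2% and 4.4% with 90% in both arms.

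**The case against.** The strongest reply is that the point rests on silence. No sentence says that the operator, or anyone told the arm, performs the follow-up examination. That is true, and the claim is limited accordingly: the text permits it. But the protocol makes a surgeon's suspicion decisive, describes no surgeons other than the four operators, and does not protect that judgement. The title pages and the text between sections III and V were not in the copy reviewed. If masking is stated there, the point falls.

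The second reply is that the harm is small. At 46 per arm the assumed gap means 2.4 against 1.8 detected hernias, and the biased single look rejects less often than full detection would (Fisher 0.7% v 1.1%; chi-square 5.6% v 5.9%). Repeat visits shrink the bias further. This stands for the significance test. It helps the estimate less: the shrinkage requires independent looks, whereas one unmasked examiner may repeat the same judgement. It also requires several visits after the hernia appears, and no end of follow-up is given.

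Third, suspicion leads to the same imaging check in both arms, so excess suspicion in one arm does not count directly as a hernia. This does narrow that route. It does nothing for hernias that go unsuspected more often in one arm, because those patients are never imaged.

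Finally, the documents do not show that a surgeon uninvolved in the operation is free at every visit. That stands, and the rostering load cannot be sized from the text.

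**Conclusion.** The concern holds. As written, the plan allows the primary endpoint to be determined by an examiner who knows the arm, so the TSH comparison is open to detection bias of unknown direction and size. The likely damage is to the estimate rather than to the test. Under the assumed 80% v 60% detection, a null effect appears as a risk ratio of 0.75 or 1.33 at a single look and moves close to 1 with four or five independent looks. The rise in false positives is small: at most 1.8 percentage points in that scenario (6.0% v 4.2%, chi-square, 92 per arm).

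The conclusion that the bias is possible rests on the text alone. Its magnitude rests entirely on assumed detection rates. Confidence is medium, because part of the protocol was not available. The sponsor should make the change, since it improves the primary endpoint at low cost, but the document does not show that bias would in fact occur.

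**What to change.** In section V and in the Follow-up paragraph, state that:

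- each follow-up examination, and the decision to request imaging, is made by one of the four trial surgeons who neither performed nor assisted at that patient's operation and does not consult the operative record beforehand;
- the closure technique does not appear on the clinic form or the imaging request;
- suspicion of TSH (yes/no), and whether the examiner already knew the arm, are recorded before the arm is disclosed.

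As a secondary addition, patients could be left unaware of their arm, which would also protect the patient-reported pain score.

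**Cost.** Clinic rostering and a masked form, with no extra staff, visits or imaging. Three of the four surgeons did not lead any given operation. If one of them assisted (an assumption, since the protocol does not say who assists), two remain eligible. The single stated skin closure should not reveal the arm.

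**Limits.** The four surgeons may talk to each other. The suture is described as "including all layers of the abdominal wall under the direct reverse vision of the defect" for the UCVA arm only, and the protocol does not say whether this can be felt on examination. Hernias that nobody suspects would still be missed; masking aims to make that loss similar in the two arms, not to remove it.
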